8.2.4 Notification of an SAE to the Ethical Committee

The sponsor shall ensure that all relevant information about suspected unexpected serious adverse reactions that are fatal or life-threatening is recorded and reported as soon as possible to the competent ethics committee, and in any case no later than seven days after knowledge by the sponsor of such a case, and that relevant follow-up information is subsequently communicated within an additional eight days.

All other suspected unexpected serious adverse reactions shall be reported to the ethics committee concerned as soon as possible but within a maximum of fifteen days of first knowledge by the sponsor. The sponsor shall also inform the other investigators.

Once a year throughout the experiment, the sponsor shall provide the ethics committee with an annual safety report, listing all suspected serious adverse reactions which have occurred over this period and a report of the subjects' safety (development safety update report). Regarding those adverse events and serious adverse reactions the investigator will take all reasonable measures, in consultation with sponsor, to protect subjects at risk following the occurrence of such events.

8.2.5 Clinical Laboratory Findings

Clinical laboratory findings are not applicable for the HERMES study.

9. Statistical considerations

9.1 Justification of sample size

In collaboration with statistical experts UGent a sample size calculation was performed. A hazard ratio of 0.5 is deemed clinically relevant, increasing the estimated 2-year SSE free survival from 20% to 45%. Assuming exponentially distributed SSE-free survival, setting alpha to 0.05 and the required power to 0.8 and assumed non-informative drop out to 20%, this results in a sample size of 120 (96 without drop out) with a required number of events of 65.

Hazard ratio (HR) = 0.5 is in between previously observed effect sizes in similar settings: Different trials analyzing the use of bone modifying agents with the presence of SREs, showing a HR around 0.7 [Smith et al; O’Carrigan et al; Rosen et al]]. In the above-mentioned phase II trial [Rosen et al] there was a large reduction in SREs from incidence from 29% to 1.6% at 1 year in the RT group. Because in our trial SSEs and not SREs will be analyzed, we expect a more conservative HR. This was also demonstrated in a trial comparing skeletal-related events with symptomatic skeletal events for two different bone modifying agents [Smith et al].

A sample size of 96 patients was calculated to have an 80% power and an $\alpha < 0.05$. With an estimated dropout of 20%, the **total sample size will be 120** with a required number of events of 65.

Each patient will be stratified by their prognostic class (0-1 vs 2), high-risk disease location (spine location vs. other) and bone modifying agents (yes vs. no) in this hierarchical order. With 3 stratification factors for randomization, there are 8 strata, which is rather high for only 60 patients per arm. Strata where only 1 arm is present and the events in these strata, are implicitly ignored in the estimation/testing. Strata with less than 10 patients will be merged with the corresponding stratum with the same value for factor A and B, but different value for C in the upfront decided hierarchical order (cfr above).

Randomization will be completed on a per patient basis (not lesion based), even though each patient may have up to 5 multiple sites of metastatic bony disease.

9.2 Population description

Patients suffering from asymptomatic or minimally symptomatic high-risk bone metastases will be screened for inclusion in this HERMES study. Data will be analyzed in accordance with the subjects' randomized treatment assignment.

9.3 Statistical methods for analysing primary and secondary outcomes

Primary objective:

The primary endpoint (SSE-free survival) is a composite endpoint of SSEs and death (death before SSE is part of the endpoint, not a competing risk). The primary endpoint is time until the occurrence of SSE in any bone metastasis or death from the date of randomization whichever occurs first. Data suggest that the median SSE-free survival is around 10.4 months. With a HR of 0.5, we hypothesize that the median SSE-free survival will be 20.8 months.

A proportion of patients will have multiple high-risk bone lesions. Pain will be reported lesion-based, however the SSE-free survival remains patient-based as this is more clinically relevant.

Secondary objectives

- The number of **hospitalizations** related to the high-risk metastase(s) will be compared between systemic therapy / observation (arm A) and upfront RT plus systemic therapy / observation (arm B) from date of study randomization to last follow-up visit (24m after randomization date), date of death of any cause or early end of participation in the study due to other reasons
- **Overall survival** will be assessed from time of study randomization to date of death of any cause or last follow-up visit (24m after randomization date)
- **Quality of life** will be compared between systemic therapy / observation (arm A) and upfront RT plus systemic therapy / observation (arm B), using the EORTC QLQ-C15-PAL questionnaire (see appendix 2) and the EuroQol Group EQ-5D-5L questionnaire (see appendix 3)
- **Adverse events** in both study arms will be evaluated using the National Cancer Institute Common Terminology Criteria for Adverse Events (NCI-CTCAE) v5.0 (see appendix 4) from the time of ICF signing to last follow-up visit (24m after randomization date), date of death of any cause or early end of participation in the study due to other reasons. Only adverse events that are related to the bone metastatic disease or related to the radiotherapy (only for patients in arm B) will be reported in the eCRF.

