SREs/SSEs are associated with pain progression and impaired **health-related quality of life (HRQoL)** and often trigger the need for analgesics, radiotherapy (RT) or surgery. In many cases, pain and quality of life cannot be fully restored with these measures. Conventional RT can achieve a clinically significant pain response in up to 80% of treated patients with a median response duration of 18–21 months [Oldenburger et al]. It is widely accepted as the standard of care for palliative treatment of uncomplicated metastatic bone pain, but is currently mainly applied once lesions become symptomatic [Steenland et al; Sze et al].

Our hypothesis is that early **RT for asymptomatic or minimally symptomatic high-risk bone metastases may have the potential to improve patient outcomes and quality of life** by reducing the number of SSEs.

A recent randomized phase II trial enrolled 74 patients to early palliative radiation versus standard of care alone to assess if early RT could decrease the incidence of SREs. Compared to standard of care, **RT resulted in a decrease in SRE incidence from 29% to 1.6% at 1 year**. Pain and need for hospitalizations were also decreased. Interestingly, RT also had a significant overall survival (OS) benefit (median OS 1y vs 1.67y (p=0.018)) compared to standard of care [Rosen et al].

Considering the striking results of this recently published phase 2 trial [Rosen et al], we will perform a **multi-centric randomized phase 3 trial to establish RT as a new treatment paradigm to prevent SSEs**. Currently, preventive radiotherapy for high-risk asymptomatic or minimally symptomatic bone metastases occurs by physician's choice and experience as phase 3 scientific evidence is missing.

We believe that preventing SSEs may have a direct impact on quality of life, cost reduction and maybe even overall survival. The benefits of palliative RT are its wide availability, its low costs and limited patient burden often in a single patient visit. In this trial, patients will be randomized to receive observation or systemic therapy or early RT in addition to observation or systemic therapy. The intervention in this study is early, upfront radiation therapy to asymptomatic or minimally symptomatic bone metastases. The aim of this trial is reducing the number of SSEs, inherently a **symptom-based endpoint**. Therefore, the hypothesis of the project is to decrease symptoms and side effects for each individual patient.

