2. Study objectives and endpoints

The primary and secondary objectives and endpoints of the study are presented in Table 2.

Table 2: Objectives and endpoints for the Hermes trial

Objectives	Endpoints
Primary	
To assess whether early preventive radiation of the high-risk asymptomatic or minimally symptomatic bone metastases in patients with metastatic cancer can decrease the number of SSEs*.	
 Time to a symptomatic skeletal related event (SSE) in any bone metastasis or death due to any cause.
Secondary	

 To evaluate the need for hospitalization related to the high-risk bone metastase(s) To assess overall survival (OS) To evaluate quality of life (QoL) 	
 The number of hospitalizations related to the high-risk bone metastases will be compared between systemic therapy/observation (arm A) and upfront RT (arm B) from date of study randomization to last follow-up visit (24m after randomization date), date of death of any cause or early end of participation in the study due to other reasons Overall survival will be assessed from time of study randomization to date of death of any cause or last follow-up visit (24m after randomization date) Quality of life will be compared between systemic therapy/observation (arm A) and upfront RT (arm B),

 To evaluate acute and late toxicity 	
using the EORTC QLQ-C15-PAL questionnaire (see appendix 2) and the EuroQol Group EQ-5D-5L questionnaire (see appendix 3)
 
 Adverse events in both study arms will be evaluated using the National Cancer Institute Common Terminology Criteria for Adverse Events (NCI-CTCAE) v5.0 (see appendix 4) from the time of ICF signing to last follow-up visit (24m after randomization date), date of death of any cause or early end of participation in the study due to other reasons. Only adverse events that are related to the bone metastatic disease or related to the radiotherapy (only for patients in arm B) will be reported in the eCRF.
---	--

*SSEs are defined as:

- symptomatic pathological fracture
- spinal cord compression leading to neurological deficit or pain
- Indication for palliative radiotherapy (for bone pain, cord compression or (impending) fracture)
- Indication for orthopedic surgery (for bone pain, cord compression or (impending) fracture)

3. Overall study design.

[figure not shown]

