5.1 Description

Patients will be randomized (1:1) to receive either systemic therapy/observation (Arm A) or early RT plus systemic therapy / observation (Arm B).

Arm A:

The observational arm (Arm A) will include **observation or systemic therapy**, according to the treating physician's discretion. Systemic therapy may include continuation of the current systemic therapy or initiation of a new systemic therapy.

These patients will be able to receive palliative RT to progressed, painful lesions (an SSE) only at the time of symptom worsening (NRS > 2/10 or need for opioids) or determination of spinal cord compression with neurological symptoms or (high risk for) fracture requiring surgical intervention. Upfront preventive RT is not allowed.

Arm B:

The intervention in this study is **early, upfront radiation therapy** to asymptomatic or minimally symptomatic (defined as high-risk) bone metastases. Up to 5 high-risk asymptomatic or minimally symptomatic metastatic locations per patient are allowed.

The radiotherapy (RT) doses used will be in accordance with common practice palliative RT schedules. As such a single fraction of 8 Gy is considered for all patients, except for patients with a very good prognosis (NRF prognostic score 0-1) in which a higher dose will be used with SABR [Chow et al].

Table 3: Predictive model for estimation of median overall survival (OS): NRF-model [Chow et al].

Three variables:

- **Primary cancer type** -> risk factor: non breast/prostate/lung cancer
- **Site of metastases** -> risk factor: metastases other than bone
- **Karnofsky performance score (KPS)** -> risk factor: KPS ≤60

0-1 risk factors	median OS 64 weeks	95%CI: 37-undefined
2 risk factors	median OS 28 weeks	95% CI 22-34
3 risk factors	median OS 10 weeks	95% CI 8-13

Simulation:

All patients will be immobilized in a comfortable and stable position to irradiate the metastatic lesion(s). Support and/or immobilization devices will be used to increase patient comfort or to ensure set-up reproducibility. A planning CT scan will be acquired without intravenous contrast with <3mm CT slice thickness (1mm for SABR) encompassing the region of interest with sufficient margin for treatment planning, a typical scan length should extend at least 10 cm superior and inferior beyond the treatment field borders. The isocenter will be placed in the middle of the affected bone lesion.

Target volume definition:

1. *Conventional radiotherapy:*

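### The hazard ratio of 0.5 for SSE or death presupposes a survival gain that the protocol does not state, and section 9.1 justifies it only by effects on skeletal events

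*Protocol*

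**What the plan says.** Section 9.1 fixes the target: "A hazard ratio of 0.5 is deemed clinically relevant, increasing the estimated 2-year SSE free survival from 20% to 45" per cent. The calculation assumes exponential SSE-free survival, "setting alpha to 0.05 and the required power to 0.8 and assumed non-informative drop out to 20" per cent, and arrives at 65 events, 96 patients, and 120 after dropout. Section 9.3 counts death before an SSE as a primary event, puts the control median at about 10.4 months, and adds: "With a HR of 0.5, we hypothesize that the median SSE-free survival will be 20.8 months".

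The support offered for 0.5 in section 9.1 is that it "is in between previously observed effect sizes in similar settings". These are HRs of about 0.7 for skeletal-related events (SREs) in trials of bone-modifying agents, and the phase II trial, described in section 1 as follows: "RT resulted in a decrease in SRE incidence from 29% to 1.6% at 1 year". Section 9.1 makes an allowance for moving from SREs to SSEs. It makes none for adding death.

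The objective in Table 2 is whether early radiotherapy "in patients with metastatic cancer can decrease the number of SSEs"; OS is a secondary objective. The survival figures in the protocol are the prognostic (NRF) table in section 5.1, with "median OS 64 weeks" for NRF 0-1 and 28 weeks for NRF 2 (both eligible), and the phase II medians of 1 and 1.67 years in section 1.

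**The concern.** A patient who is alive and SSE-free is alive, so the SSE-free curve lies on or below the OS curve. The planned arm B curve has a median of 20.8 months and 45% at 2 years, above what any OS figure in the protocol allows. If radiotherapy does what the objective says, preventing SSEs without changing mortality, the deaths remain as events in both arms and pull the composite HR towards 1.

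Two things are at stake. A real SSE benefit could be missed because the power quoted belongs to a larger effect. A positive result could also come largely from deaths, leaving the question about SSEs open. The blinded look in section 9.4 would not reveal the problem: it estimates the event rate, and deaths fill the event count whether or not the HR is diluted.

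**Working it through.** **Reproducing the plan.** Events = 4 × (1.96 + 0.842)² / (ln 0.5)² = 65.3, against 65 stated (two-sided alpha 0.05, 1:1). Power at 65 events = Φ(√65/2 × 0.693 − 1.96) = 79.8%. With 2-year SSE-free survival of 0.20 and 0.20^0.5 = 0.447, the event probability at 24 months is 1 − (0.20 + 0.447)/2 = 0.676, so 96 patients give 64.9 events, and 96/0.8 = 120. Medians of 10.4 and 20.8 months give 20.2% and 44.9% at 24 months. The planned figures agree with each other.

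**Inputs for the check.** The control SSE-free median is 10.4 months (section 9.3). Median OS is 28 and 64 weeks (section 5.1), or 28 × 12/52.18 = 6.4 and 64 × 12/52.18 = 14.7 months. The phase II medians are 12 and 1.67 × 12 = 20.0 months (section 1). Exponential OS is my assumption; the protocol assumes it only for SSE-free survival.

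**Formulas.** If no SSE occurs in arm B, its event hazard is its death hazard, so the lowest possible HR = 10.4 / (arm B median OS in months). Two-year OS = 0.5^(24/median). Power = Φ(√65/2 × |ln HR| − 1.96).

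| Arm B median OS taken from | Months | 2-year OS | Lowest HR | Power, 65 events |
|---|---|---|---|---|
| NRF 2 | 6.4 | 7.6% | none below 1 (OS is already under 10.4 months) | – |
| Phase II control | 12.0 | 25% | 0.87 | 8% |
| NRF 0-1 | 14.7 | 32% | 0.71 | 29% |
| Phase II radiotherapy arm | 20.0 | 43.6% | 0.52 | 75% |
| Needed for HR 0.5 | 20.8 (about 90 weeks) | 44.9% | 0.50 | 80% |

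All four cited medians are below 20.8 months, and all four 2-year values are below 45%. At HR 0.707 (the NRF 0-1 row), 80% power would need 261 events.

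**Incomplete prevention.** At a 64-week OS with mortality unchanged, preventing 90%, 70% or 50% of SSEs gives HR 0.74, 0.79 or 0.85, and power of 23%, 15% or 9%.

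**Survival gain required.** Even with every SSE prevented, arm B median OS must reach 20.8 months. From 12 months that is 8.8 months (death HR 12/20.8 = 0.58); from 14.7 months it is 6.1 months (14.7/20.8 = 0.71). The phase II difference was 8.0 months (12/20.0 = 0.60).

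**Counter-check.** Take 29% and 1.6% as 1-year cumulative incidences of a first SSE, keep the 10.4-month control median, and hold the rate of death before an SSE equal in both arms. The control composite hazard is ln 2/10.4 = 0.0666 per month, and 1 − exp(−12 × 0.0666) = 0.551. The control SSE hazard is 0.29/0.551 × 0.0666 = 0.0351, leaving 0.0315 for death first. The arm B SSE hazard solving to 1.6% is 0.0016. HR = (0.0016 + 0.0315)/0.0666 = 0.498, power 80%. This implies an arm B median OS of about 21 months and a death rate after an SSE about 4 times (control OS 64 weeks) to 12 times (control OS 12 months) the rate before one.

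**The case against.** Power is always conditional on the target effect. Section 9.1 declares 0.5 the clinically relevant HR, and everything computed from it is right. That stands: there is no arithmetic error.

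The protocol also gives grounds for expecting a mortality effect. The phase II medians imply a death HR of about 0.60. Applied to a 64-week control OS, this lowers the floor to 0.71 × 0.60 = 0.42, so SSE prevention would not need to be complete; at a 12-month control OS the floor is 0.52. Section 1 says that preventing SSEs might even lengthen survival, and the counter-check shows that HR 0.50 follows if SSEs strongly raise mortality. This stands too, but it confirms that 0.5 needs a survival effect, which sections 9.1 and 9.3 do not mention.

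The NRF table is a prognostic tool used for eligibility, stratification and the radiotherapy scheme, not a planning assumption. Its NRF 0-1 interval runs from 37 weeks to undefined, so the 90 weeks needed lies inside it. The mix of classes is not given, nor is the source of the 10.4 months. A reader might therefore infer too much: that HR 0.5 is unreachable, or that the trial is likely to fail. The documents support neither, because both depend on point estimates and on mortality staying unchanged.

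Finally, section 7.2 lists a comparison of the number of SSEs between arms, and component analyses are often left to an analysis plan. But the endpoints are fixed in this document, and neither Table 2 nor section 9.3 names an SSE endpoint separate from death.

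**Conclusion.** The point holds as a mismatch between the assumed effect and the composite endpoint. On the OS figures the protocol cites, HR 0.5 requires arm B survival at least about as long as in the phase II radiotherapy arm, which is a gain of roughly the phase II size, and near-complete SSE prevention at that survival. This is not stated, and the SRE effects in section 9.1 do not justify it for SSE or death. With mortality unchanged and every SSE prevented, power at 65 events is about 29% at a 64-week median OS and 8% at 12 months; with the phase II radiotherapy-arm OS it is 75%.

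These figures assume exponential OS, the planned 10.4-month control median and two-sided alpha. They do not show that the 80% is miscalculated: it is correct for a composite HR of 0.50. What is missing is the condition under which that HR can arise.

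**What to change.** In sections 9.1 and 9.3:

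- State that 80% power holds only for a composite HR of 0.50 that includes an effect on mortality, and give the power at 65 events for HR 0.60 (54%), 0.65 (41%) and 0.70 (30%).
- Replace the rationale based on SRE effects with one for SSE or death, saying how much of the effect is expected from each component.
- Name time to first SSE, with death as a competing event, as a secondary endpoint (cause-specific HR and cumulative incidence), here and in Table 2, so that the SSE objective is answered separately from deaths.
- Optionally, have the blinded look in section 9.4 also report the pooled split between SSE-first and death-first events.

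The cost is protocol wording and one extra analysis on SSE and survival data already being collected. The stated power will look less favourable.

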- e. Health related quality of life parameters will be reported by subjects using the EORTC QLQ-C15-PAL and EQ-5D-5L questionnaires
- f. All pain -and anticancer medications (including corticoid therapy) and bone-modifying agents used during the study will be recorded. The dates of administration, method of administration, dosage, and reason for use will be included.
- g. A month can be 28, 29, 30 or 31 days, depending on the month.
- h. Occurrence of an SSE during the study should be reported to the study team immediately. In case an SSE occurs, the assessments that should take place during the next follow-up visit, should be completed at that time point, preferentially within one week. These assessments must be documented in the eCRF. Furthermore, the type of SSE (e.g. symptomatic pathological fracture,...) needs to be registered. In case of fracture or compression, the location and planned treatment must also be documented. In case of RT or surgery, the location and reason must be registered. Afterwards, only survival data will be recorded on the date of the planned FU visits until 24m after the randomization date as well as possible occurrence of another SSE within 24m after the randomization date.

Clinical Trials Oncology

Ref.Nr.: P.01-S.23

Versie: 6.0

- i. During the study (from time of study randomization to date of death of any cause or last follow-up visit (24m after randomization date) or early end of participation in the study due to other reasons), hospitalizations related to the high-risk bone metastase(s) should be documented in the eCRF. More specifically, the hospital admission date and date of discharge will be recorded as well as whether the hospitalization is related to an SSE (if yes, it should be specified to which SSE).

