- j. For each SAE, it should be evaluated whether it concerns an SSE. If it concerns an SSE, the SAE should be documented as such in the eCRF and the necessary actions should be taken (see footnote h). In case hospitalization occurs, it should be evaluated whether the hospitalization is related to the high-risk metastase(s) and this information should be documented in the eCRF. Note that only (S)AE related to the bone metastatic disease or related to radiotherapy (only applicable for arm B) must be reported in the eCRF and that all SSE need to be registered in both study arms, including an SSE in a bone metastasis that was not previously included in the study (only applicable for arm B). An exception are SSE's in bone metastases that were already treated with surgery or RT before study participation.
- k. In case of discontinuation of a subject's participation without withdrawal of consent, only survival data will be collected at the remaining follow-up timepoints (i.e. 1m, 3m, 6m, 12m, 18m and 24m after randomization date) and the occurrence of an SSE will be registered in the eCRF if it occurs within 24m after the randomization date.
- l. Patients in the upfront RT arm developing new minimally symptomatic or asymptomatic high-risk bone metastases during study participation are strongly advised to further be treated with preventive RT. Details concerning the characteristics of these new high-risk metastases as well as details regarding the preventive RT must be captured in the eCRF.

Clinical Trials Oncology

Ref.Nr.: P.01-S.23

Versie: 6.0

Administrative structure

Study responsible physician:	[name] Iridium Netwerk Department of Radiation Oncology [name]
Project managers:	Clinical Trials Office (CTO), Oncologisch Centrum ZAS [contact], [contact] [contact] www.clinicaltrials oncology.be
Sponsor	ZAS vzw, [name] [contact] www.zas.be

1. Background & Rationale

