6.2 End of study

The end of the study is defined as the date when the last follow-up visit takes place (i.e. 24 months after date of randomization of the last participant if his/her participation was not discontinued early)

In case an SSE occurs, the assessments that should take place during the next follow-up visit, should be completed at that time point, preferentially within one week. These assessments must be documented in the eCRF. Furthermore, the type of SSE (e.g. symptomatic pathological fracture,...) needs to be registered. In case of fracture or compression, the location and planned treatment must also be documented. In case of RT or surgery, the location and reason must be registered. Afterwards, only survival data and possible occurrence of another SSE will be recorded on the planned FU visits until 24m after the randomization date.

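### The protocol contradicts itself on whether hospitalisations are still recorded after a first SSE

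*Protocol*

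**What the plan says.** The hospitalisation endpoint has one window wherever it is defined. In Protocol section 9.3, the number of hospitalisations "related to the high-risk metastase(s) will be compared between systemic therapy / observation (arm A") and the upfront RT arm. Section 9.3 counts admissions "from date of study randomization to last follow-up visit (24m after randomization date), date of death of any cause or early end of participation" for other reasons, and the synopsis and Table 2 agree. None of them lists a first SSE as an end.

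Footnote i of the Schedule of events gives the matching collection rule: over the same period, "hospitalizations related to the high-risk bone metastase(s) should be documented in the eCRF". It asks for admission and discharge dates "as well as whether the hospitalization is related to an SSE (if yes, it should be specified to which SSE").

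Footnote h of the same table covers what happens once an SSE occurs. The next visit's assessments are brought forward, and then: "Afterwards, only survival data will be recorded on the date of the planned FU visits until 24m after the randomization date", together with any further SSE in that period. Section 6.2 repeats the rule: "Afterwards, only survival data and possible occurrence of another SSE will be recorded on the planned FU visits until 24m after the randomization date". Neither place names hospitalisations among the items that continue.

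The safety sections have no stop at an SSE. Section 8.2.2 documents related (S)AEs in both arms to 24 months, death or early exit. Section 8.2.1 asks that any hospitalisation be assessed for its relation to the high-risk metastases.

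**The concern.** Two current rules give a site different instructions for the same patient. Under footnote i, an admission four months after a first SSE is entered. Under footnote h or section 6.2, it is not among the data still recorded. In a multicentre trial, sites may settle this differently.

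The loss would not be balanced. SSEs are what upfront RT is meant to prevent, so if the hypothesis is right, arm A loses more post-SSE time than arm B. Admissions after an SSE are also a large part of what an endpoint on the need for hospitalisation should capture. This belongs in the protocol and not in the analysis plan, because no model can restore admissions that were not recorded.

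**Working it through.** **Inputs.** Section 9.3: "Data suggest that the median SSE-free survival is around 10.4 months", and 20.8 months is hypothesised for arm B. Section 9.1: exponential times, HR 0.5, 2-year SSE-free survival 20% versus 45%. Section 3.2.1: 24 months of follow-up per patient. The protocol gives no admission rate and no split of the primary events between SSE and death.

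**Check of the plan's own figures.** With h = ln 2 / median, h_A = 0.0667 and h_B = 0.0333 per month. 24-month SSE-free survival is exp(−24h) = 0.202 and 0.449, which agrees with the stated 20% and 45%.

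**Observed time under the literal reading of footnote h and section 6.2.** If recording stops at first SSE or death, the expected observed time within 24 months is (1 − exp(−24h))/h:

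- Arm A: (1 − 0.202)/0.0667 = 11.97 months
- Arm B: (1 − 0.449)/0.0333 = 16.52 months
- A/B = 0.725 and B/A = 1.38

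At equal constant monthly admission rates, arm A would show 1 − 0.725, or about 28%, fewer admissions per patient. A true rate in arm A up to 1.38 times that in arm B would be hidden.

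**Does the order of the arms reverse?** Admissions are unlikely to occur at a constant rate unaffected by SSEs. An illustration with assumed inputs shows what matters: OS median 30 months in both arms (death hazard 0.0231), 0.01 admissions per month before an SSE, 40% of first SSEs leading to admission, and 0.06 per month afterwards.

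- SSE hazard = h − 0.0231: 0.0435 (A) and 0.0102 (B).
- Probability of a first SSE within 24 months = SSE hazard × observed time: 0.0435 × 11.97 = 0.52 (A) and 0.0102 × 16.52 = 0.17 (B).
- Mean time alive within 24 months = (1 − exp(−24 × 0.0231))/0.0231 = 18.42 months in both arms, so mean post-SSE time is 6.45 (A) and 1.90 (B).

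| Admissions counted | Arm A | Arm B |
|---|---|---|
| Before the SSE only | 0.01 × 11.97 = 0.12 | 0.01 × 16.52 = 0.17 |
| Plus the SSE's own admission | 0.12 + 0.4 × 0.52 = 0.33 | 0.17 + 0.4 × 0.17 = 0.23 |
| Plus all later ones to 24 months | 0.33 + 0.06 × 6.45 = 0.72 | 0.23 + 0.06 × 1.90 = 0.35 |

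The order reverses only in the first row. In the second row it is right, but the A/B ratio shrinks from about 2.1 (0.72/0.35) to about 1.4 (0.33/0.23).

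**Window ending only at death or 24 months (section 9.3 and footnote i).** With equal survival and equal exit there is no imbalance. The phase II OS medians quoted in section 1 (1 and 1.67 years, that is 12 and 20.04 months) would give 12.98 versus 16.31 months, A/B 0.80. Arm A OS medians of 28 or 64 weeks (section 5.1, Table 3) with an assumed OS HR of 0.6 to 1.0 give A/B from 0.70 to 1.00.

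**The case against.** The strongest reply is that footnotes h and i do different jobs. Footnote h limits what is done at planned visits, while footnote i is the specific rule for admissions as events and plainly expects SSE-related admissions to be captured. The safety rules support this: in-patient hospitalisation is an SAE criterion (8.1.2), related SAEs are documented to 24 months (8.2.2) and reported within 24 hours (8.2.3), and each hospitalisation is assessed for its relation to the metastases (8.2.1, footnote j).

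Much of this stands. A reader might infer that footnote h shortens the endpoint window to the first SSE. The documents do not support that, because no endpoint definition does so. It is also not established that post-SSE admissions will go uncollected.

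The conflict remains all the same. Footnote h and section 6.2 list what continues after an SSE. The list includes an event-type item, a further SSE, and omits hospitalisations. The SAE route is not a full substitute either: section 8.2.3 exempts some situations from SAE reporting, such as rehabilitation without an untoward occurrence.

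Footnote k is not part of the conflict. It limits collection after a patient leaves the study ("In case of discontinuation of a subject's participation without withdrawal of consent, only survival data will be collected at the remaining follow-up timepoints", plus SSEs), and the endpoint window ends at early exit anyway.

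**Conclusion.** The contradiction is real and should be resolved. Footnote h and section 6.2 conflict with footnote i, the synopsis, Table 2, section 9.3 and the safety rules in 8.2.1 and 8.2.2. If sites follow footnote h or section 6.2 literally, admissions are lost more often in the arm with more SSEs, and that arm's count is biased downward. The 28% is an illustration. It rests on the literal reading, the design medians, exponential times and equal constant admission rates.

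Three stronger readings go too far:

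- That the arm with more SSEs will look better. This needs true rates within a factor of about 1.38 under the constant-rate illustration, or an SSE-triggered admission that is not counted. Footnote i asks for that admission.
- That a survival difference already biases the count. The phase II medians are background, not design assumptions, and equal survival gives no imbalance.
- That the absence of a rate model is a defect. The analysis plan is not shown and may specify one.

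The endpoint is secondary. The primary analysis and its sample size are unaffected.

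**What to change.** Amend footnote h and section 6.2 to state that hospitalisations related to the high-risk bone metastases continue to be recorded, with admission and discharge dates, until 24 months, death or early end of participation, regardless of SSE. This brings both places into line with footnote i and section 9.3. The cost is a sentence in two places and a note to sites, since footnote i already asks for the dates. It should be done early, because admissions that go unrecorded may not be recoverable later.

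As advice only, since the analysis plan may already do so: compare admissions relative to time at risk, with death accounted for, because the count window also ends at death or exit. This would not replace the amendment, as it cannot recover uncollected admissions.
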